8.2.1 Reporting of Serious Adverse Events (SAEs) to GSK

The Investigator shall report all SAEs to GSK within 24 hours after becoming aware of the SAE. SAEs should be reported to GSK using the paper SAE reporting form. After completion, the form should be scanned and emailed to the SAE contacts (Medical Monitor and GSK Italy pharmacovigilance) found at the beginning of the protocol on the Sponsor/Medical Monitor Contact Information page.

In rare circumstances if email communication is not available, notification by telephone is acceptable, with a copy of the SAE form sent by overnight mail.

The following is added to the protocol:

8.2.2. Regulatory Reporting Requirements for SAEs

Prompt notification by the Investigator to GSK of SAEs related to study treatment (even for non-interventional post-marketing studies) is essential so that legal obligations and ethical responsibilities towards the safety of subjects and the safety of a product under clinical investigation are met.

GSK has a legal responsibility to notify both the local regulatory authority and other regulatory agencies about the safety of a product under clinical investigation. GSK will comply with country specific regulatory requirements relating to safety reporting to the regulatory authority, Institutional Review Board (IRB)/Independent Ethics Committee (IEC) and investigators.

Investigator safety reports are prepared for suspected unexpected serious adverse reactions according to local regulatory requirements and GSK policy and are forwarded to Investigators as necessary.

An Investigator who receives an investigator safety report describing a SAE(s) or other specific safety information (e.g., summary or listing of SAEs) from GSK will file it with the IB and will notify the IRB/IEC, if appropriate according to local requirements.

The following text has been removed from the protocol:

8.2.3. Suspected Unexpected Serious Adverse Reaction (SUSAR) *In case of SAR that is unexpected, the Investigator/Sponsor must report the reaction as soon as possible (and in any case no later than 7 days for reactions that are fatal or life-threatening, and no later than 15 days for all other SUSARs) to the competent Regulatory Authorities and to the competent Ethics*

Committee (and that relevant follow up information is subsequently communicated within an additional eight days).

8.2.4. Periodic reporting Once a year throughout the trial, the Investigator should provide to Competent Regulatory Authorities and the Ethics Committee an Annual Safety Report, that is a listing of all suspected SAR, which have occurred over this period and a report of the subjects' safety.

11. Page 86: Section 10.2 . Documentation of data in the case report form (CRF)

The following wording has been removed from the protocol:

It is the responsibility of the Investigator to maintain adequate and accurate CRFs to record all observations and other data pertinent to the clinical investigation. All CRFs should be completed in their entirety in a neat, legible manner to ensure accurate interpretation of data; a black ball point pen should be used to ensure the clarity of reproduced copy of all CRFs. Should a correction be made, the information to be modified must not be overwritten. The corrected information will be transcribed by the authorized person next to the previous value and dated.

The following wording has been added to the protocol:

It is the responsibility of the Investigator to maintain adequate and accurate CRFs to record all observations and other data pertinent to the clinical investigation.

Under TIGET sponsorship paper CRFs will be utilized; these should be completed in their entirety in a neat, legible manner to ensure accurate interpretation of data; a black ball point pen should be used to ensure the clarity of reproduced copy of all CRFs. Should a correction be made, the information to be modified must not be overwritten. The corrected information will be transcribed by the authorized person next to the previous value and dated.

Under GSK sponsorship an electronic CRF will be implemented; all data previously collected on paper CRF and all data collected following sponsorship transfer will be entered into GSK defined CRFs. All these data will transmitted electronically to GSK or designee and combined with data provided from other sources in a validated data system.

Management of clinical data will be performed in accordance with applicable GSK standards and data cleaning procedures to ensure the integrity of the data, e.g., removing errors and inconsistencies in the data.

Adverse events and concomitant medications terms will be coded using MedDRA (Medical Dictionary for Regulatory Activities) and an internal validated medication dictionary, GSKDrug.

CRFs (including queries and audit trails) will be retained by GSK, and copies will be sent to the investigator to maintain as the investigator copy. Subject initials will not be collected or transmitted to GSK according to GSK policy.

16.3. Appendix 3: Summary of Significant Changes Introduced by Protocol Amendment Version 10

A list of all changes contained in this amendment are included below:

1. Date and protocol amendment number has been changed
2. Medical Monitor/Sponsor Information has been changed. An Orchard Therapeutics Medical Monitor and PPD SAE contact have been added given Orchard Therapeutics role as regulatory sponsor.
3. Sponsor Legal Registered Address has been added
4. Orchard Therapeutics Sponsor signatory page has been added
5. Orchard Therapeutics investigator protocol agreement page has been added
6. PPD has been added to the abbreviation/acronym list
7. Global changes made to protocol include:
 - a. The acronym GSK has been changed to Orchard Therapeutics as regulatory sponsor.
 - b. For the reporting of SAEs section, the acronym GSK has been changed to PPD.
 - c. For the section on collection of pregnancy information, the acronym GSK has been changed to PPD.
 - d. The protocol header number has been removed and name has been changed to Orchard Therapeutics.

16.4. Appendix 4: Summary of Significant Changes Introduced by Protocol Amendments Version 11 and 11.1

A list of significant changes contained in version 11 are listed below.

Throughout: text has been amended to allow all subjects to enter a separate observational long-term follow-up (OLTFU) study once it is set up and subjects been followed up for a minimum of 5 years, not just after subjects enter the (extended long-term follow-up) ELTFU phase. As part of the OLTFU study, patients will continue to be followed up for a total of 15 years from the date of treatment with gene therapy.

Throughout: text has been added to allow patients to attend remote visits (upon agreement by PI, medical monitor and sponsor,) and text has been added to describe these remote visits. Text has also been added to allow informed consent (performed by the PI or a person designated by the PI) to take place remotely.

Throughout: the severity assessments used for clinical events including bleeding, infections and eczema have been clarified upon FDA feedback.

8.4.1. Replication competent lentivirus (RCL): the strategy for RCL testing was simplified. In the previous version of the protocol, 3 assays (ELISA for HIV p24 antigen on serum, DNA PCR for VSV-G envelope on cells, and RT-PCR for HIV-pol RNA on serum) were used for first line detection of RCL. In the amended text, one test is performed in the first instance (HIV p24 antigen detection in the serum by ELISA), in line with EMA guideline CHMP/BWP/2458/03, which defines the best assays for the determination of RCL. Detection of HIV p24 antigen in serum by ELISA is identified as a validated and sensitive test, which is also routinely used in the clinic to determine HIV positivity in case of suspected viral infection by the wild type lentivirus. Should this test be positive, further analyses will be performed, including the two remaining tests mentioned above (DNA PCR for VSV-G envelope on cells, and RT-PCR for HIV-pol RNA on serum). If a positive result is obtained from at least one of the additional tests, an appropriate confirmatory test may be performed. This change is required since some of the commercially available tests to detect RNA-Pol HIV (e.g. Roche COBAS Ampliprep/COBAS Taqman HIV-1 v2.0 Test), are unable to differentiate between the DNA of gene corrected cells and HIV infection, potentially leading to false positive results.

Minor readability and typographical errors were corrected in the text

The following changes are contained in version 11.1:

Medical Monitor/ Sponsor information page: Contact details for the Medical Monitor and for pharmacovigilance SAE reporting have been updated to reflect changes in personnel and vendor.

Throughout: PPD (former pharmacovigilance vendor) was replaced by Sponsor/ Sponsor's pharmacovigilance designee.

Table 8c: The mention of 'special interest' was removed from the definition of events such as bleeds, infections, autoimmunity, eczema and suspected malignancies, which are disease related and do not meet the criteria for events of special interest in terms for PV safety analysis and reporting.

16.5. Appendix 5: Summary of Significant Changes Introduced by Protocol Amendments Version 12

A list of significant changes contained in version 12 are listed below.

a. the name of the previous Sponsor (Orchard Therapeutics) has been replaced with the name of the new Sponsor (Fondazione Telethon ETS) in the text.

HSCT	Hematopoietic stem cell transplantation
ICH E9	International Conference on Harmonization Statistical Principles for Clinical
ICH E3	International Conference on Harmonization Structure and Content of
ISA	Integration Site Analysis

ITT	Intention to Treat
IVIG	Intravenous Immunoglobulin
LV	Lentiviral
LVV	Lentiviral Vector
mAb	Monoclonal Antibodies
MPV	Mean Platelet Volume
NCI	National Cancer Institute
PIP	Paediatric Investigation Plan
PB	Peripheral Blood
MedDRA	Medical Dictionary for Regulatory Activities
SOC	System Organ Class
PT	Preferred Term
PBSC	Peripheral Blood Stem Cells
RCL	Replication Competent Lentivirus
SAE	Serious Adverse Event
SAS	Statistical Analysis Software
SD	Standard Deviation
SI	Stimulation Index
SAP	Statistical Analysis Plan
SDTM	Study Data Tabulation Model
VCN	Vector Copy Number
VSV-G	Vesicular stomatitis virus
WAS	Wiskott-Aldrich Syndrome
WASP	Wiskott-Aldrich Syndrome Protein

WHO	World Health Organization
WHO-DD	World Health Organization Drug Dictionary

3 Introduction

As per ICH E9 “Statistical Principles for Clinical Trials”, the purpose of this document is to provide a more technical and detailed elaboration of the principal features of the analysis described in the protocol. This document describes the rules and conventions to be used in the presentation and analysis of efficacy and safety data for Protocol TIGET-WAS. It describes the data to be summarised and analysed, including specifics of the statistical analyses to be performed.

This statistical analysis plan (SAP) is based on protocol version 12, dated 19 Sep 2023.

4 Study Objectives, Endpoints

4.1 Primary Objective

1. To evaluate the safety of the administration of autologous CD34⁺ cells transduced with a lentiviral vector containing the Wiskott-Aldrich Syndrome (WAS) protein gene in subjects with WAS, after a reduced intensity conditioning regimen;
2. To evaluate the long-term engraftment of WASP-expressing transduced cells;
3. To evaluate the efficacy of gene therapy assessed as:
 - a. Improvement of the subject's immune function, specifically of T cell function and antigen-specific responses to vaccinations;
 - b. Improvement of thrombocytopenia.

4.2 Secondary Objectives

To evaluate the efficacy of gene therapy (OTL-103) in improving the subject's clinical conditions assessed by a reduction in frequency of severe infections, and bleeding episodes and reduction of auto-immunity phenomena and eczema.

4.3 Safety Objectives

The safety objectives of the study are contained within the Primary Objectives outlined above in Section 4.1.

5 Study Methods

5.1 General Study Design and Plan

This is a non-randomized, open label, single centre, phase I/II, prospective study involving a single infusion of autologous CD34⁺ cells transduced with a 3rd generation VSV-G pseudo typed lentiviral vector in 8 subjects diagnosed with WAS without a suitable matched donor for allogeneic transplant or ineligible for hematopoietic stem cell transplantation (HSCT).

[figure not shown]
Five protocol phases are foreseen, after signature of the informed consent:

1. Screening phase, during which the conditions required by the clinical protocol for subjects' enrolment will be assessed and fulfilment of the inclusion/exclusion criteria of the study will be evaluated;
2. Baseline phase, carried from the end of the screening phase to the day before the harvest of peripheral blood stem cells, if performed, or the day before rituximab administration (day -22);
3. Treatment phase, from the end of the Baseline phase to day 1 (day of OTL-103 infusion);
4. Follow Up phase: the Follow Up phase is composed of an Initial Follow Up period of at least 3 years, when patients are intended to reach the primary efficacy timepoint, and then a further Long -Term Follow Up period from 3 up to 8 years. ;
5. Extended Long-Term Follow-Up (OLTFU) phase: patients who complete the Follow-up phase will then be contacted annually, in order to collect long-term safety and selected efficacy data, until a separate observational long-term follow-up (OLTFU) study is initiated and patients have enrolled in it.

Once the OLTFU study is set up, patients will be invited to enter the OLTFU study at any time after they have completed a minimum of 5 years follow up in this study (WAS Pivotal, 201228). As part of the OLTFU study, patients will continue to be followed up for a total of 15 years from the date of treatment with gene therapy.

Screening and baseline phases will be summarised as pre-treatment in the analysis outputs.

Figure 1 Trial Flow Chart

The schedule of events can be found in [Appendix 3](#) and is as per Section 7 of the protocol. After gene therapy treatment there are 12 visits over the first 36 months and then one visit annually from year 4 to year 8 (5 visits), unless a subject is transferred to the OLTFU after year 5 but prior to year 8.

5.2 Randomisation and Blinding

As this is a non-randomised open label study, no randomisation or blinding is required.

5.3 Derived variables

5.3.1 Reference Start Date and Study Day

Study Day will be calculated from the reference start date and will be used to show start/ stop day of assessments and events.

Reference start date is defined as the day of infusion of transduced CD34+ cells (Day 1).

- If the date of the event is on or after the reference start date then:
Study Day = (date of event – reference date) + 1.
- If the date of the event is prior to the reference start date then:
Study Day = (date of event – reference date).

In the situation where the event date is partial or missing, Study Day and any corresponding durations will be presented based on the imputations specified in Section 7.3.1.

5.3.2 Baseline

For all endpoints the baseline value will be the last assessment prior to treatment phase, unless otherwise stated.

5.3.3 Retests, Unscheduled Visits and Early Termination Data

All visits (scheduled and unscheduled) will be windowed per Table 1 (Section 5.3.5).

Early termination data will be mapped to the next available visit number (as per visit schedule for each specific assessment) for by-visit summaries.

In the case of a retest (same visit number assigned), the earliest available measurement for that visit will be used for by-visit summaries.

Listings will include scheduled, unscheduled, retest and early discontinuation data.

5.3.4 Common Calculations

Change from baseline is defined as:

Post-Treatment Visit Value – Baseline

Person years observation (PYO) is calculated as the total observation period across all subjects within the given study period. The calculation will be made as below:

$$\text{Person years observation} = \sum_{i=1}^n \frac{(period\ end\ date)_i - (period\ start\ date)_i + 1}{365.25}$$

Where i is the individual subject and n is the total number of subjects with observation in the period.

The calculation of duration of follow-up is defined as:

Date of Study Completion Visit - Gene Therapy Treatment date+1

Where subjects are ongoing at interim analyses the study completion date is substituted with the data cut point.

Calculation of time to discontinuation of Intravenous Immunoglobulins (IVIG), platelet infusions and antimicrobial treatment is defined:

Date of Last Respective Treatment – Gene Therapy Treatment Date + 1

For patients where treatment has yet to stop this will be summarised as ongoing.

Unless otherwise stated, if the baseline value is missing, then the change from baseline will also be set to missing.

Baseline of platelet count is defined as the median of the (at least three) determinations performed before beginning of treatment.

5.3.5 Windowing Convention

All visits (scheduled and unscheduled) will be windowed as per the tables below.

Early termination data will be mapped to the next available visit number (as per visit schedule for each specific assessment) for by-visit summaries.

In the case of a retest (same visit number assigned), the earliest available measurement for that visit will be used for by-visit summaries.

Listings will include scheduled, unscheduled, retest and early discontinuation data.

The following tables describe the windowing conventions used for various purposes of the TFLs.

Table 1 Windowing for Treatment Phases

Assigned Study Day (Inclusive)		Visit Assigned
From	To	
Informed Consent	Screening Date	Screening
Screening Date +1	PBSC Mobilization Date -1, if performed Day before Rituximab administration	Baseline*
PBSC Mobilization, if performed	Date of GT (if administered) or date of EoS for subjects that did not receive GT	Treatment
Day of Rituximab administration		
2	11	Day 7
12	18	Day 14
19	26	Day 21
27	46	Day 30
47	76	Day 60
77	136	Day 90
137	273	Day 180
274	457	Year 1
458	639	Year 1.5
640	822	Year 2
823	1004	Year 2.5
1005	1278	Year 3
1279	1644	Year 4
1645	2009	Year 5
2010	2374	Year 6
2375	2739	Year 7
2740	3104	Year 8
3105	-	Final Assessment

* Efficacy measurements taken on the same day as PBSC mobilisation will be considered for baseline efficacy measures.

Screening and baseline periods will be grouped as pre-treatment in some outputs

Pre-treatment and on-treatment windowing will be defined separately for groups of data. For adverse events and concomitant medication data these will be defined below.

Table 2 Windowing for treatment phases; AEs and Concomitant Medications

Assigned Study Day (Inclusive)		Visit Assigned
From	To	
Screening date	Treatment phase start date -1	Pre-treatment
Treatment phase start date (see Table 2)	Date of GT (if administered) or date of EoS for subjects that did not receive GT	On-treatment
2	183	0-6 Months Follow-up
184	366	6-12 Months Follow-up
367	731	1-2 Years Follow-up
732	1097	2-3 Years Follow-up
1098	2923	3-8 Years Follow-up
2924	End of study	>8 Years Follow-up
2	End of Study	Post-Treatment

Severe infections and bleeding events will be classified according to the time of occurrence relative to treatment as in the Table 3 below. This classification will be used in displays containing severe infections and bleeding events data only. For AE displays including severe infections and bleeding events, the treatment phases for AE data defined in Table 2 will be followed.

Table 3 Windowing for treatment phases; Severe Infections, Bleeding Events and hospitalisations

Assigned Study Day (Inclusive)		Visit Assigned
From	To	
-365	-1	Pre-treatment
2	183	0-6 months follow-up
184	366	6-12 months follow-up
367	731	1-2 Years Follow-up
732	1097	2-3 Years Follow-up
1098	2923	3-8 Years Follow-up
2924	End of study	>8 Years Follow-up
184	End of study	> 6 months Follow-up

Windowing will be applied to the data prior to any missing data calculations.

6 Sample Size

Given the low frequency of disease and the degree of novelty of the proposed experimental approach, we plan to treat overall 8 patients, in an estimated 5-year period.

7 General Considerations

All study patients will be included for evaluation until the earliest time point of the following: completion of a minimum of 5 years follow up in this study (TIGET-WAS) and transition to a separate OLTFU study, death, withdrawal or loss to follow up. Patients who, at 1 year after gene therapy, show absence of transduced cell engraftment in peripheral blood and bone marrow will be subsequently evaluated for safety aspects only.

At the end of the study, when all subjects have completed a minimum of 5 years follow up and transitioned to a separate OLTFU study, a final statistical analysis will be performed with all data available up to the transition to the OLTFU study, and a final clinical study report will be compiled.

The final analyses will be performed after all required database cleaning activities have been completed and final database freeze and database release has been declared by Data Management (DM).

The default significance level will be 5%; confidence intervals will be 95% and all tests will be two-sided. As this study is not powered all p-values and confidence intervals will be nominal.

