4.3.2. Secondary efficacy endpoints

a) *Longitudinal analyses of sustained engraftment of genetically corrected hematopoietic stem cells in peripheral blood and/or in bone marrow and expression of vector derived WASP*

Presence of gene corrected cells and WASP expression will be assessed at the time points shown in [Table 8a](#) and [Table 8b](#), as described above.

b) Analyses of sustained multilineage engraftment of genetically corrected cells in peripheral blood and/or in bone marrow

Presence of gene corrected cells assessed by quantitative PCR on all the available peripheral blood and/or bone marrow cell subpopulations (BM subpopulations: GlyA+, CD15+, CD3+, CD19+, CD56+; PB subpopulations: CD15+, CD19+, CD56+) at 1, 2 and 3 years after gene therapy. The availability of all the subpopulations depends on the amount of samples and on the technical procedures.

Adequate engraftment is defined as ≥0.04 VCN/cell (equivalent to 4% assuming a VCN of 1).

c) *Reduced frequency of severe infections*

Decrease in number of severe infections as evaluated starting from the first year follow up visit and thereafter until the 3-year visit after the treatment, by , complete physical examinations, hematological and microbiological tests compared to clinical history from the 12 months prior to GT. Infections will be assigned a CTCAE grading (as described in Section [4.3.2.1](#)) by the Investigators, identical to how severity grading was used in clinical history.

d) *Reduced bleeding episodes*

Reduction in bleeding manifestations when present, as assessed starting from the first year follow up visit and thereafter until the 3-year visit, by clinical monitoring, compared to clinical history from 12 months prior to GT. Information about bleeding will be recorded through follow up by collecting data from parents, clinical reports periodically sent by local doctors following the patients at home and by clinical evaluations performed at each follow up visit at our center. Data will be recorded in the patients' clinical charts. Bleeding events will be given CTCAE grading (as described in Section [4.3.2.1](#)) by the Investigators, identical to how severity grading was used in clinical history.

e) *Reduced autoimmunity phenomena and eczema*

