10.2.2.1 Summaries of All Adverse Events

Adverse events, unless otherwise stated, will be summarised according to the phase in which the AE started, such that an AE with a duration spanning more than one study phase is only reported once. Adverse event tables will summarise data recorded on Relevant Medical History, Concomitant Diseases and Adverse Event pages. Adverse events that were recorded from day of gene therapy will be recorded on the adverse event page, with prior events recorded on the relevant medical history and concomitant diseases pages.

An overall summary of AEs will be presented including severity, relatedness and seriousness of events. The total number and percentage of subjects reporting AEs will be summarised by MedDRA System Organ Class (SOC), preferred term (PT) and the treatment phase at which they were initially reported. In addition, the total number and percentage of subjects reporting treatment-related AEs during each treatment phase will be summarised by SOC and preferred term. Unexpected adverse reactions (UARs) and suspected unexpected severe adverse reactions (SUSARs) will be summarised by SOC, PT and treatment phase. Expected adverse reactions are listed in protocol section 8.2.4. A separate summary of AEs by severity, SOC and preferred term will be presented.

The total number of AEs, and the number and percentage of AEs with an outcome of recovered/resolved within each treatment phase will be summarised. In addition, a summary of the most frequently reported AEs (defined as rate greater than 1 per year of patient observation in any treatment phase) will be presented by treatment phase and preferred term. A summary will also be presented of AE preferred terms by treatment phase ordered by decreasing frequency.

Clinical events of CTC grade 3 or above that occurred in the 12 months prior to gene therapy will be summarised as part of the pre-treatment medical history next to those that occurred after gene therapy.

A listing of all AEs will be provided. A listing of the relationship between SOC, PTs and verbatim text will also be provided. Based on the PTs, a separate listing will be produced for AEs related to bleeds, infections, autoimmunity, eczema or suspected malignancies to be reviewed together with results from a manual search.

A listing will be created of any events leading to discontinuation.

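### SAP Table 3 follows the protocol's 12-month comparator, but its Pre-treatment row takes in 22 to about 73 treatment-phase days and infusion Day 1 falls in no row

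*SAP*

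**What the plan says.** SAP 5.3.5 sets out three windowing tables. For the third it says "Severe infections and bleeding events will be classified according to the time of occurrence relative to treatment as in the Table 3 below". Its rows are Pre-treatment (Day -365 to -1), 0-6 months (Day 2 to 183), later follow-up rows, and an overlapping row for everything from Day 184. The table title also names hospitalisations, and SAP 9.1.6 and 9.3.1 apply the table to platelet infusions and antimicrobials.

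The 365 days have a clear source. Protocol 4.3.2 has severe infections "compared to clinical history from the 12 months prior to GT" and gives bleeding the same reference period. SAP 8.3, 9.2.3 and 9.2.8 repeat it. SAP 5.3.5 also allows for different windows: "Pre-treatment and on-treatment windowing will be defined separately for groups of data".

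Elsewhere the label means something narrower. SAP 5.1 says "Screening and baseline phases will be summarised as pre-treatment in the analysis outputs", and the note under Table 1 says "Screening and baseline periods will be grouped as pre-treatment in some outputs". Table 1 starts the treatment phase at stem-cell mobilisation, or at rituximab if there is none, and ends it on the date of gene therapy. Table 2 closes Pre-treatment the day before that phase and has an On-treatment row that includes the infusion date.

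On day numbering, SAP 5.3.1 says "Reference start date is defined as the day of infusion of transduced CD34+ cells (Day 1"), and SAP 14 confirms that there is no Day 0. SAP 10.2.2.1 says "Adverse events that were recorded from day of gene therapy will be recorded on the adverse event page".

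**The concern.** One label covers two different periods. Under Table 3, Pre-treatment contains the whole treatment phase up to the day before infusion. Those days have content. Protocol 8.2.3 records events from mobilisation, harvest and chemotherapy as Concomitant Diseases, and SAP 9.2.3, 9.2.4 and 9.2.8 draw infections, bleeds and hospitalisations from that page. Protocol 6.6 foresees platelets before procedures. Protocol 6.11 starts pentamidine on day -30, and SAP Appendix 2 counts pentamidine as an antimicrobial. Protocol 6.10 describes an admission averaging 60 days that begins with chemotherapy, and SAP 9.2.8 does not say how its days before infusion are handled. All of this counts as baseline burden in the Table 3 rates.

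Separately, an event on the infusion day is collected but has no Table 3 row.

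The trial is uncontrolled with 8 patients, so these before/after rates carry the efficacy contrast for infections, bleeding and hospitalisation. A reader of the rates cannot tell background disease from treatment-phase burden.

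Three cross-references add to the risk that programmers window the same events differently:
- SAP 9.2.3 points to Table 4, which defines analysis sets.
- Table 2 points to itself ("Treatment phase start date (see Table 2") for a date that Table 1 defines.
- SAP 9.2.4 uses Table 2 for the bleeding pie charts, although 5.3.5 assigns bleeding-only displays to Table 3.

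**Working it through.** **The plan's own window.** Day -365 to Day -1 inclusive is -1 - (-365) + 1 = 365 days. By the SAP 5.3.4 person-years formula, 8 patients give 8 × 365/365.25 = 7.99 person-years, assuming that all are at least 12 months old at infusion. The 12 months are reproduced.

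**Coverage.** Checking every valid study day from -365 onward against the Table 3 rows leaves one day unassigned: Day 1.

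**Treatment-phase days inside the window.**
- Rituximab start (day -22): 22 days, 22/365 = 6.0%.
- Mobilisation 5-10 weeks before infusion (one reading of the Protocol Table 7 footnote): 35 to 70 days, 9.6% to 19.2%.
- Mobilisation 5-10 weeks before harvest on day -3 (Protocol 6.2 and 6.3): 38 to 73 days, 10.4% to 20.0%.

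The mobilisation figures are approximate. The protocol gives the interval only roughly and allows a repeat procedure. Counting from a first G-CSF dose assumed to be 6 days before collection would turn 73 into 79.

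**Effect on the baseline rate.** Let s be the share above and k the ratio of the treatment-phase rate to the background rate. The documents give no value for k, so it is an assumption. The tabulated baseline rate is the background rate times (1 - s) + k·s = 1 + s(k - 1).

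| k | s = 6.0% | s = 20.0% | Apparent post/pre ratio if there is no true effect |
|---|---|---|---|
| 0.5 | 0.97 | 0.90 | 1.03 to 1.11 |
| 1 | 1.00 | 1.00 | 1.00 |
| 2 | 1.06 | 1.20 | 0.94 to 0.83 |

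A narrower assumption lets k apply only on days with a scheduled drug. Protocol Table 7 lists day -22, days -20 to -18 (optional ATG) and days -3 to -1, which is 7 days. At most 7 G-CSF days bring this to 14, or 14/365 = 3.8%, and k = 2 then gives ×1.04.

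**Single events.** One treatment-phase event adds 1/7.99 = 0.125 per person-year to baseline. The 0-6 month row holds 8 × 182/365.25 = 3.99 person-years, so one Day 1 event placed there would be 1/3.99 = 0.25 per person-year.

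**Consequences of splitting off the treatment phase.**
- Baseline falls from 7.99 to 8 × 343/365.25 = 7.51 person-years (22 days removed), or to between 8 × 330/365.25 = 7.23 and 8 × 292/365.25 = 6.40 (35 to 73 days removed).
- For a given rate, the standard error of the log rate grows by 1/√(1 - s): about 3% with a rituximab start and 5-12% with mobilisation.
- An On-treatment row through Day 1 holds 8 × 23/365.25 = 0.50 to 8 × 74/365.25 = 1.62 person-years.
- Days removed per mobilised patient with no scheduled mobilisation or conditioning drug: 35 - 14 = 21 to 73 - 14 = 59.

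**The case against.** The strongest reply is that the window is pre-specified. The protocol fixes 12 months before gene therapy for infections and bleeding, SAP 9.2.8 glosses its pre-treatment phase in those terms, and 5.3.5 lets data groups differ. This stands. A reader might infer that Table 3 departs from the protocol, and it does not. What remains is the reused label and the absence of a row that isolates the treatment phase.

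A second reply is that the events are not hidden. The adverse-event tables draw on all three record pages (SAP 10.2.2.1), use Table 2 with its On-treatment row, and include a summary by severity and phase (Table 14.3.2.2.7). Day 1 events also appear in the 48-hour listing. This stands too, and it limits the point to the Table 3 rates.

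Third, the Day 1 gap does not affect the protocol's comparison for infections and bleeding, which begins at the first-year visit (Protocol 4.3.2, 9.6, 9.7). It concerns only the early SAP rows.

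Fourth, the comparisons are secondary, supportive or exploratory, and nominal, and the shift is small beside sampling error. With an assumed 8 events in 7.99 person-years, the exact Poisson 95% interval is 0.43 to 1.97 per person-year. That argues for a modest remedy, not for none.

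**Conclusion.** The point holds in limited form. Table 3 implements the protocol comparator, but its Pre-treatment row mixes in 6.0% treatment-phase time with a rituximab start, or about 9.6-20.0% with mobilisation, and Day 1 is unassigned. The Table 3 rates for infections, bleeding, hospitalisations, platelet infusions and antimicrobials are all affected.

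A reader might infer that the baseline is inflated and the therapy flattered. For infections and bleeding the documents give no treatment-phase rate, so the sign is unknown and the size depends wholly on the assumed k.

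For platelet infusions and antimicrobials, peri-procedural use and prophylaxis tend to raise the before rate. It is tempting to put a figure on this, but pentamidine continues after infusion (Protocol 6.11). If the counting rule in SAP 8.4 applies, ongoing courses also count in the follow-up rows. No net size can be quoted.

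**What to change.** 1. Keep Day -365 to -1 as the main comparator and relabel it *12 months before GT*.
2. Add an *On-treatment* row to Table 3, from the Table 1 treatment-phase start through Day 1. Footnote that it overlaps the 12-month row and is not summed with it, as the row from Day 184 already overlaps others. Show counts beside rates.
3. Add one sensitivity before/after rate with baseline ending the day before the treatment phase starts, removing those days from both events and person-years. Apply it to infections, bleeding, hospitalisations, platelet infusions and antimicrobials.
4. Correct the SAP 9.2.3 reference from Table 4 to Table 3 and the Table 2 self-reference to Table 1. State which table governs the bleeding pie charts in 9.2.4.
5. Record the changes in SAP 14.

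The cost is SAP wording, one row and one extra rate per display; the person-years formula already works from per-patient period dates. The sensitivity rate is less precise by the 3-12% shown above and discards about 21-59 days per mobilised patient that may be ordinary disease background. The On-treatment rates, on at most 1.62 person-years, will be unstable. The sensitivity baseline will still contain catheter admissions from the baseline phase (Protocol 6.10) and, with a rituximab start, prophylaxis on days -30 to -23.
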